7.2.6. Equipment

Medtronic will control the supply of investigational devices and study materials (e.g., Investigator Site File, eCRF access). The final study implant using investigational devices occurred in February 2023. First investigational device shipment at each site occurred after the Principal Investigator (PI) and key site personnel who handle storage of the device completed all device training and documented on the Delegated Task List. Medtronic will not provide any study-specific equipment to the sites.

Study sites should follow their institutional procedures for maintenance of echocardiography and laboratory equipment used for assessing the study variables.

7.3. Study trial

The objective of this study is to evaluate the safety and efficacy of the Medtronic CoreValve™ Evolut™ PRO System when used by Chinese implanting centers in patients with severe symptomatic aortic stenosis (AS) who are at high risk for Surgical Aortic Valve Replacement (SAVR).

The study population includes males and females with severe symptomatic aortic stenosis who are considered at high risk for SAVR.²⁴

8. Indications, contraindications and precautions of the investigational product

The Medtronic Evolut PRO system is intended for relief of aortic stenosis in patients with symptomatic heart disease due to severe native calcific aortic stenosis who are judged by a heart team, to be at high risk for open heart surgery in the evaluation of the Evolut PRO China Clinical Study. The TAV treats aortic stenosis by displacing and functionally replacing the dysfunctional native valve with a bioprosthetic valve delivered on a catheter while the heart is still beating, thus avoiding the risks of cardiopulmonary bypass. ^{25,26,27,28} Its intended performance is to relieve aortic valve stenosis without inducing significant regurgitation, thereby restoring effective aortic valve function.

Refer to the Investigator's brochure (IB) and Instructions for Use (IFU) document for intended use, indications and contraindications. See IFU also for mechanism of action, manufacturing information, model numbers, device identification, storage and handling requirements, summary of training and experience, description of medical procedures, and list of potential risks and warnings.

9. Overall design

9.1. Study design

This is a prospective, observational, single arm, interventional, multicenter, post-market study. The subjects will continue to be followed through 5 years. The study objective will be assessed by evaluating the primary and secondary endpoints at 30 days.

Version 5.006-Oct-2023

Page 25 of 121

Medtronic

9.1.1. Study objectives and/or Endpoints

9.1.1.1. Study Objective(s)

The objective of this clinical study is to evaluate the safety and efficacy of the Medtronic CoreValve™ Evolut™ PRO System when used by Chinese implanting centers in patients with severe symptomatic aortic stenosis (AS) who are at high risk for Surgical Aortic Valve Replacement (SAVR).

9.1.1.2. Primary Endpoints

The following primary endpoints will be used to evaluate the study objective:

Safety

All-cause mortality at 30 days

Efficacy

• The percentage of evaluable echocardiograms with moderate or severe aortic regurgitation at 30 days by transthoracic echocardiography (TTE).

9.1.1.3. Secondary Endpoints

The following secondary endpoints will be used to evaluate the study objective:

Safety

- 1) The VARC II¹ Combined Safety Endpoint at 30 days, which includes the following components:
 - All-cause mortality
 - All stroke (disabling and non-disabling)
 - Life-threatening bleeding
 - Acute kidney injury: stage 2 or 3 (including renal replacement therapy)
 - Coronary artery obstruction requiring intervention
 - Major vascular complication
 - Valve-related dysfunction requiring repeat procedure (BAV, TAVI, or SAVR)
- 2) Event rates of the individual components of the VARC II composite safety endpoint at 30 days
- 3) New permanent pacemaker at 30 days

Efficacy

1) Device success at 24 hours to seven days, defined as¹:

MDT18065EVR009 Version 5.0 06-Oct-2023 Page 26 of 121 Medtronic

- Absence of procedural mortality, AND
- Correct positioning of a single prosthetic heart valve into the proper anatomical location,
 AND
- Intended performance of the prosthetic heart valve, defined as the absence of patientprosthesis-mismatch and mean aortic valve gradient less than 20 mmHg (or peak velocity <3m/sec), AND absence of moderate or severe prosthetic valve regurgitation
- 2) Valve performance parameters at 30 days by transthoracic echocardiography (TTE):
 - Mean aortic gradient
 - Effective orifice area
 - Degree of aortic regurgitation (transvalvular, paravalvular, total)

9.1.1.4. Other Outcome Measures

- 1) Event rates of the following TAVI-related complications:
 - a. change to surgery
 - b. need for cardiopulmonary mechanical assistance
 - c. coronary occlusion or obstruction
 - d. annular rupture or dissection
 - e. ventricular perforation
 - f. mitral valve damage
 - g. prosthetic valve displacement, migration, or embolism
 - h. acute kidney injury (up to 7 days post procedure)
- 2) All-cause mortality at 6 months, one year, and annually through 5 years
- 3) All stroke (disabling and non-disabling) at 6 months, one year, and annually through 5 years
- 4) Myocardial infarction at 30 days, 6 months, one year, and annually through 5 years
- 5) Life-threatening bleeding at 30 days, 6 months, one year, and annually through 5 years
- 6) New AV-Conduction disturbances (LBBB and RBBB) at 30 days
- 7) Prosthetic valve endocarditis at 30 days, 6 months, one year, and annually through 5 years
- 8) Prosthetic valve thrombosis at 30 days, 6 months, one year, and annually through 5 years
- 9) Valve-related dysfunction, defined as moderate or severe prosthetic valve stenosis, or moderate or severe prosthetic regurgitation (per VARC II) at one year and annually through 5 years
- 10) Valve-related dysfunction requiring repeat procedure at 30 days, 6 months, one year, and annually through 5 years
- 11) Valve hemodynamic performance metrics by Doppler echocardiography at one year and annually through 5 years

MDT18065EVR009 Ve

Version 5.006-Oct-2023

Page 27 of 121

Medtronic

- a. Mean aortic gradient
- b. Effective orifice area
- c. Degree of aortic regurgitation (transvalvular, paravalvular, total)
- 12) New York Heart Association (NYHA) functional classification at 30 days, 6 months, one year and annually through 5 years
- 13) Post-operative EQ-5D quality of life at 30 days and one year

9.1.2. Selection of study method and rationale

The basis for the selection of these endpoints includes the following considerations:

- 1) They are clinically relevant and address the most important safety and efficacy aspects of the Evolut PRO and associated implant procedure
- 2) They are objectively defined and measurable in all subjects
- 3) They are consistent with current recommendations for endpoints in TAVR clinical studies.¹
- They follow the NMPA "Guidelines for Clinical Trials of Trans-catheter Aortic Valve Implantation" (2019-03-01)²⁹

Collectively, the 30-day endpoints and all the data collected through 5 years will provide a valid assessment to determine if the established safety and efficacy of the Evolut PRO system can be replicated by Chinese implanting centers in Chinese patients with severe symptomatic aortic stenosis at high risk for SAVR.

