5.1. Objectives

The objective of this study is to evaluate the safety and efficacy of the Medtronic CoreValve™ Evolut™ PRO System when used by China implanting centers in Chinese patients with severe symptomatic aortic stenosis (AS) who are at high risk for Surgical Aortic Valve Replacement (SAVR).

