With the completion of all Primary Endpoint visits and analyses in the Evolut PRO China Study and considering the product registration status in China, the Evolut PRO China Clinical Study will be transitioned from a pre-market study to a post-market study status effective with Clinical Investigation Plan Version 5.0.

The objective of this clinical study is to confirm that the established safety and efficacy of the Evolut PRO System, inclusive of the system component models outlined in Section 7.1, can be replicated by Chinese implanting centers in Chinese patients with severe symptomatic aortic stenosis, inclusive of both tricuspid and bicuspid anatomy (Sievers classification type 1), who are deemed at high risk for SAVR. Data from this study may be used to support license registration for new generation(s) or expanded indication(s) of the study devices in China.

7. Characteristics, structure and composition, operating principle, mechanism of action and range of trial of the investigational product

For overview of the Medtronic CoreValve™ Evolut™ PRO System, see also the Investigator's Brochure (IB) which includes preclinical testing and clinical data of this investigational product.

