10.1. Statistical design, method and analysis procedures

This is a prospective, single arm, multi-center, interventional, post-market study. The primary endpoints are all-cause mortality and the percentage of evaluable echocardiograms with moderate or severe prosthetic aortic valve regurgitation at 30 Days. As this is not a powered hypothesis-driven study, the sample size was not determined by statistical methods. The sample size is consistent with the 50 subject minimum as outlined NMPA TAVI Clinical Trial Guideline²⁹.

Subjects who are taken to the procedure room and attempt the implantation will comprise the study population evaluated for the study objectives and associated endpoints. Data from subjects enrolled as roll-ins will not be combined with the primary analysis cohort and will be analyzed separately. The analysis subsets for the study endpoints are shown in Figure 5.

[figure not shown]

Figure 5. Analysis sets for the study endpoints

There are 2 main analysis sets for the primary study population:

- 1. **Attempted implant set.** Includes all subjects who are brought into the procedure room and any of the following have occurred: anesthesia administered, vascular line placed, TEE placed, or any monitoring line placed.
- 2. **Implanted set.** Includes all subjects who are implanted with the Evolut PRO, defined as the Evolut PRO is placed in the aortic annulus and completely released from the delivery catheter system.

Statistical analysis of primary and secondary endpoints was performed when the primary study population (n= 50 subjects with attempted implant, exclusive of "roll-in" patients) were followed for 30 days. Results for the baseline characteristics and the primary and secondary endpoints from the 60-subject TAVR 2.0 US Clinical Study (Evolut PRO) will be provided for descriptive comparison. In addition, results will be descriptively compared to available results for other commercially approved TAVR systems in China.

Data will be analyzed and Clinical Study Reports (CSRs) will be prepared for the primary endpoint (at 30 days) and for the final analysis. The final analysis will be performed when all implanted subjects have completed their 5-year follow-up. Annual CSRs may also be prepared after the primary endpoint and prior to the final analysis CSRs, per the discretion of the Sponsor.

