10.5. Criteria for acceptability/unacceptability of clinical trial results

Statistical analysis was performed by the leading site with collaboration support and oversight from the Sponsor for primary and secondary endpoint analysis. Statistical analysis of the primary endpoints was performed when the primary study population (n= 50 subjects with attempted implant, exclusive of "roll-in" patients) were followed for 30 days. Results for the baseline characteristics and the primary and secondary endpoints from the 60-subject TAVR 2.0 US Clinical Study (Evolut PRO) will be provided for descriptive comparison. Criteria for acceptability/unacceptability is not applicable as this is not a powered hypothesis-driven study. At the time of the primary endpoint analysis, the leading site was consulted to review the clinical trial results for acceptability/unacceptability.

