13.3. Risk-Benefit Rationale

The Evolut PRO system has been studied in pre-market and post-market clinical studies in the United States, Europe and other countries. TAVR with the Evolut PRO system has been shown to be a safe and effective treatment for patients with severe aortic stenosis who are at high risk or greater for operative mortality with surgical aortic valve replacement (SAVR).

Available pre-market and real-world clinical evidence on TAVR in tricuspid and bicuspid patients has demonstrated that implantation of the Evolut R and Evolut PRO transcatheter aortic valves can be accomplished by multiple operators with a high degree of technical success and with an acceptably low level of procedural complications. Results demonstrated comparable outcomes for bicuspid patients as compared to tricuspid patients who were deemed at increased risk for SAVR (intermediate and above). This study is designed to confirm the safety and efficacy of the Evolut PRO system in the Chinese patient population. Although there are risks to the study subjects for participation in the study, they are anticipated to be similar to the risks of undergoing TAVR outside of the study. The study endpoints are clinically relevant and consistent with the study objectives. The overall study design is confirmed with the NMPA TAVI Guideline²⁹ was confirmed during the NMPA consultation meetings and protocol synopsis submitted with no further objections/feedback (October 2018 through March 2019). Therefore, the study as described is justified.

MDT18065EVR009

Version 5.006-Oct-2023

Page 55 of 121

Medtronic

Measures to Mitigate Risks to Study Subjects

The following measures were and will be implemented to minimize risks to the study subjects:

- Implanting physicians had experience with TAVR
- Implanting physicians underwent didactic and simulator training prior to the study start at each site
- Patients will be rigorously followed over the course of the study

Alternatives

Presently, therapeutic alternatives for patients with the clinical indication targeted for the Evolut PRO system include the following:

- Medical therapy
- Balloon aortic valvuloplasty
- Surgical aortic valve replacement
- TAVI with another device approved in China

14. Quality control of clinical trial

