#### Hypothesis/Decision criteria:

No specific hypotheses or pass/fail criteria have been set. The analysis will be descriptive, and no statistical hypothesis test will be performed.

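### The protocol says the study will confirm or determine replication in China, but no hypothesis, margin, reference rate or pass/fail rule is set, so the design can only estimate rates

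*Protocol*

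**What the plan says.** The aim is worded in two strengths.

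- **Stronger.** Protocol Section 6 (background, last paragraph): "The objective of this clinical study is to confirm that the established safety and efficacy of the Evolut PRO System" can be reproduced in Chinese centres and patients. Section 9.1.2: the data "will provide a valid assessment to determine if the established safety and efficacy of the Evolut PRO system can be replicated". Section 13.3: "This study is designed to confirm the safety and efficacy of the Evolut PRO system in the Chinese patient population".
- **Weaker.** Protocol 5.1: "The objective of this study is to evaluate the safety and efficacy of the Medtronic CoreValve™ Evolut™ PRO System". Protocol 7.3 and 9.1.1.1 and SAP Section 4 also say only *evaluate*.

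The statistical sections support only the weaker aim. Protocol 10.3 rules out formal testing, and 10.2 says that 50 attempted implants follows a regulatory guideline and not a calculation. For both primary endpoints (SAP 7.10.1 and 7.10.2) the SAP states: "No specific hypotheses or pass/fail criteria have been set".

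Protocol 10.5 states: "Criteria for acceptability/unacceptability is not applicable as this is not a powered hypothesis-driven study". Its next sentence says that, at the primary endpoint analysis, "the leading site was consulted to review the clinical trial results for acceptability/unacceptability". The same section says that the leading site performed the statistical analysis, with sponsor support and oversight.

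Protocol 10.1 promises a descriptive comparison with the 60-subject US study of the same device. It adds that "results will be descriptively compared to available results for other commercially approved TAVR systems in China". The SAP contains neither comparison, although SAP 7.13 says that its analyses are aligned with the protocol.

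**The concern.** A statement that something has been confirmed or replicated needs a rule: how close to which reference value counts as the same. Without one, a reader of the study report cannot tell which results would have counted as failure to replicate, and similarity is judged after the rates are known.

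This matters beyond this report. Protocol Section 6 says that the data may support registration of new device generations or expanded indications, and Section 22 says that the study reports may support new generations. The 30-day analysis is complete, but the final report and any annual reports are still to come, so what the trial claims can still be set right.

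**Working it through.** **1. Is there any criterion to apply?** The elements that a replication claim would need:

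| Element | Protocol | SAP |
|---|---|---|
| Hypothesis or test | None (10.3) | None (7.10) |
| Pass/fail rule | Not applicable (10.5) | None (7.10.1, 7.10.2) |
| Reference rate | US study named, rates not given (10.1, 10.5) | US study absent |
| Margin or definition of similar | Similarity anticipated, not defined (12.1, 12.2) | None |

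There is no planned figure to reproduce: the documents give no alpha, power, margin or expected rate, and they do not claim that 50 was calculated.

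**2. What can 50 subjects show?** Event counts below are illustrative, because the documents do not give the results. The exact two-sided 95% upper limit solves P(X ≤ x | 50, p) = 0.025. For x = 0 it is 1 − 0.025^(1/50) = 7.1%.

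| Events in 50 | Rate | Exact 95% interval | SAP log-log Kaplan-Meier interval, no censoring |
|---|---|---|---|
| 0 | 0% | 0 to 7.1% | undefined |
| 1 | 2% | 0.05 to 10.6% | 0.3 to 13.4% |
| 2 | 4% | 0.5 to 13.7% | 1.0 to 15.1% |

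The last column uses the method in SAP 7.2.2. For one death, S = 0.98 and the Greenwood standard error is √(0.98 × 0.02/50) = 0.0198. On the log-log scale this is 0.0198/(0.98 × |ln 0.98|) = 1.00, and the limits are 1 − 0.98^exp(±1.96). With no deaths, ln S = 0 and the interval cannot be computed.

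For the echo endpoint the denominator may be smaller. If 45 echoes were evaluable (an assumption), the exact upper limit would be 7.9% with 0 events and 15.2% with 2.

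**3. Would a low count distinguish true rates?** The chance of at most 1 event in 50 is 74% if the true rate is 2%, 40% if it is 4% and 19% if it is 6% (binomial; the rates are assumptions).

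**4. Against the US study (n = 60).** For 0/50 v 0/60, the Wilson upper limits are z²/(n + z²): 3.84/53.84 = 7.1% and 3.84/63.84 = 6.0%. The Newcombe interval for China minus US is therefore −6.0 to +7.1 points. For 1/50 v 1/60 it is −7.0 to +8.9 points.

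**5. Does 50 rule out every replication conclusion?** No; it depends on the criterion, and none is stated. Suppose the rule were that the exact upper limit must fall below a threshold, with a true rate of 2%:

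- Threshold 10%: only 0 events pass; the chance is 0.98^50 = 36%.
- Threshold 15%: at most 2 events pass; the chance is 92%.
- Threshold 20%: at most 4 events pass; the chance is 99.7%.

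For two-group non-inferiority at a 2% rate (one-sided 0.025, 80% power), n per group = (1.96 + 0.84)² × 2 × 0.02 × 0.98/margin². This gives 342 for a 3-point margin, 124 for 5 points and 31 for 10 points.

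**The case against.** The strongest reply is that the limitation is disclosed. The protocol and SAP say repeatedly that the study is not powered or hypothesis-driven, the formal objective is to evaluate, and 95% intervals are planned for both primary endpoints. On this view the sentence in 9.1.2 only explains why the endpoints were chosen, and it refers to 5-year data as well as 30-day counts. Bias is also limited: an independent committee adjudicates deaths and endpoint-related events, an independent core laboratory read the echocardiograms through 30 days, and SAP Section 8 requires independent validation of the primary endpoints. All of this stands, and it makes the point one about claims rather than about the integrity of the estimates. It does not justify *confirm* or *determine*, because the later data have no replication criterion either.

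Three stronger readings are tempting and are not supported.

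- A reader might infer that the leading site decided whether the results were acceptable. Protocol 10.5 says only that it was consulted. No verdict is recorded, and the basis of the consultation is not described. Section 11.1.4 ties that site's analysis role to local regulations and study requirements.
- A reader might infer that 50 subjects cannot support any replication conclusion. Step 5 shows that this depends on a margin that nobody set: 50 is too few for margins of 3 to 5 points, but could meet a loose threshold of 15 to 20%.
- A reader might infer that 50 is a sample-size error. It is openly attributed to the guideline minimum.

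The systems for the second comparison in 10.1 are unnamed. That is missing detail and does not carry this point.

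**Conclusion.** The point holds as a mismatch between claim and design. The confirming and determining language in Protocol Sections 6, 9.1.2 and 13.3 has no criterion behind it, and the study as planned supports estimates with intervals only.

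The size is this: an upper 95% limit of about 7% with no events and about 14% with two, and an excess over the US study of about 7 points still possible when neither study has an event. These figures assume 50 analysed subjects, no censoring and illustrative counts. The China-minus-US interval is unadjusted and compares separate cohorts.

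Two lesser points also hold. The two statements on acceptability in 10.5 do not fit together, and the US comparison promised in 10.1 is missing from a SAP that declares itself aligned.

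**What to change.** 1. **Wording.** In Protocol Sections 6, 9.1.2 and 13.3 and in future study reports, replace confirming or determining replication with estimating, with 95% confidence intervals. State that no replication conclusion is drawn. Do not add a pass/fail criterion now: enrolment and the primary analysis are complete, so it would be post hoc.
2. **SAP comparison.** Add the comparison with the 60-subject US study, labelled descriptive, unadjusted and specified after the primary analysis. Give each difference a 95% interval suited to the endpoint:
   - Newcombe for binary proportions (moderate or severe regurgitation, device success).
   - A Kaplan-Meier difference interval for time-to-event rates, with a named score or exact method when there are zero events.
   - A mean difference for gradient and effective orifice area.
3. **Protocol 10.5.** Reconcile the two statements on acceptability and document the basis of the leading site's consultation, without presenting it as an acceptance decision.

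The cost is text changes to the protocol, SAP and reports, plus one table; no new patient data are needed. The drawback for the sponsor is a less favourable headline claim.

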9.1.3. Measures for reducing and avoiding deviation

The study methods include the following measures to minimize potential sources of bias:

- 1) An Eligibility Review Committee (ERC) confirms subject eligibility and anatomical suitability.
- An independent Clinical Events Committee (CEC) will review and adjudicate, at minimum, all deaths and endpoint related adverse events. Safety endpoint results will be based on CEC adjudications.
- 3) All sites will follow a standardized protocol for acquisition of echocardiographic endpoint data.
- 4) An independent Echo Core Lab was utilized to evaluate echocardiograms through 30 days.
- 5) Study sites should follow their institutional procedures for maintenance of echocardiography and laboratory equipment used for assessing the study variables.

9.1.4. Investigational medical device and controlled medical device/diagnosistherapeutic method (if any)

The Evolut PRO Transcatheter Aortic Valve Replacement (TAVR) System is the investigational device that will be evaluated in this single-arm clinical study.

MDT18065EVR009

Version 5.006-Oct-2023

Page 28 of 121

Medtronic

Note: Effective 24-DEC-2021, National Medical Products Administration (NMPA) approved the Medtronic CoreValve™ Evolut™ PRO System for the treatment of severe aortic stenosis for symptomatic patients in China who are at high or extreme risk for open heart surgery. Overseas clinical data were utilized to support product registration. The Evolut PRO System is commercially available during the Evolut PRO China Clinical Study enrollment period. However, only Evolut PRO System components that are labeled investigational (i.e., "Clinical trial use only") were used in the study. Commercial Evolut PRO System components were not used in the study. After all study attempted implants occurred and the primary endpoint analysis was completed, the Evolut PRO China Study was converted from a pre-market to a post-market study via implementation of Clinical Investigation Plan (CIP) Version 5.0.

